## 2. Glossary

Term	Definition
ADE	Adverse Device Effect
AE	Adverse Event
AC	Advisory Committee
ASADE	Anticipated Serious Adverse Device Effect
CDSCO	Central Drugs Standard Control Organization
CIP	Clinical Investigation Plan
CMP	Clinical Management Plan
CRS	Clinical Research Specialist
CTA	Clinical Trial Agreement
CV	Curriculum Vitae
CVD	Cardiovascular Disease
DCGI	Drug Controller General of India
DD	Device Deficiency
DMC	Data Monitoring Committee
DRF	Data Release Form
DTL	Delegated Task List
EC	Ethics Committee
ECG	Electrocardiogram/Electrocardiography
eCRF	Electronic Case Report Form
EDC	Electronic Data Capture
FU	Follow Up
GCP	Good Clinical Practice

Term	Definition
HF	Heart Failure
IRB	Institutional Review Board
LAD	Left Atrial Diameter
LVEDD	Left Ventricular End Diastolic Diameter
LVEF	Left Ventricular Ejection Fraction
LVOTO	Left Ventricular Outflow Tract Obstruction
MACCE	Major Adverse Cardiac & Cerebrovascular Event
MI	Myocardial Infarction
MR	Mitral Regurgitation
MS	Mitral Stenosis
MV	Mitral Valve
NYHA	New York Heart Association
PI	Principal Investigator (one per site)
PIC	Patient Informed Consent
RDC	Remote Data Capture
SADE	Serious Adverse Device Effect
SAE	Serious Adverse Event
SAM	Systolic Anterior Motion
SOP	Standard Operating Procedure
TEE	Transoesophageal Echocardiograph
TTE	Transthoracic Echocardiograph
UADE	Unanticipated Adverse Device Effect
USADE	Unanticipated Serious Adverse Device Effect

### 3. Synopsis

Title	PRESERVE - MITRAL P rospective R egistry to S tudy C linical O utcom E s of R epair of M itral V alv E s in South Asia.
Clinical Study Type	Post Market Registry
Product Name	Profile 3D™, CG Future®
Sponsor	Medtronic plc. Clinical Research [name]
Regional Sponsor	[name] India- Medtronic Pvt. Ltd. [name]
Indication under investigation	Patients suffering from mitral valve disease and indicated for a mitral valve repair procedure with Profile 3D™ and CG Future® annuloplasty system as part of standard of care, in accordance with the product label indications (instructions for use), contraindications, and warnings
Investigation Purpose	There is limited local evidence on mitral repair products in South Asia and a prospective post market registry will provide real world data on clinical outcomes
Product Status	Profile 3D™ and CG Future® annuloplasty systems are indicated for the reconstruction and/or remodeling of the pathological mitral valve. The devices are approved and commercially available in India and are commercially available in Bangladesh and Nepal.
Primary Objective(s)	The objective of this registry is to gather data on the clinical outcomes of Medtronic mitral repair products (Profile 3D™ and CG Future® annuloplasty systems) in the approved intended use up to 12 months from the day of procedure
Secondary Objective(s)	Characterize the demographics of the patients undergoing mitral valve repair using annuloplasty systems in India, and assess the functional

# PRESERVE-Mitral Clinical Investigation Plan

MDT16016SUR002

Version 1.0, dated 10-APR-2017

Page 10 of 58

Medtronic

	and procedural outcomes of the procedure.
Study Design	PRESERVE-Mitral Registry is a prospective non-randomized, non-interventional, post-market registry.
Sample Size	200
Inclusion/Exclusion Criteria	
Inclusion Criteria:
 

1. Patients with valvular insufficiency and/or stenosis and indicated for the reconstruction and/or remodeling of pathological mitral valves with Profile 3D™ and CG Future® annuloplasty systems

2. Indications and contraindications provided in the product Instructions for Use

3. Subject is 18 years of age or older

4. The patient or his/her Legally Authorized Representative (LAR) has been informed about the nature of the registry and the patient informed consent for study participation has been obtained prior to performing any study-related procedures from the subject or Legally Authorized Representative, as per applicable local requirements

 
Exclusion Criteria:
 

1. Contraindications as per IFU:

a. Heavily calcified valves

b. Valvular retraction with severely reduced mobility

c. Active bacterial endocarditis

2. Aortic valve replacement as concomitant procedure

3. Already participating in another clinical study, possibly leading to bias and jeopardizing the scientific appropriate assessment of the study endpoints

Study Procedures and Assessments	

• Baseline/Pre-Operative (data from most recent assessment before planned implant date preferred, not exceeding 60 days)

• Implant

• Discharge (date of discharge or 7 days post procedure, whichever comes first)

• 3 to 6 months (data reported from 90 days up to 210 days post procedure, whichever comes later)

• 12 months (data reported up to day 395 (365 +/- 30 days) post procedure date will be collected)

Safety Assessments	All relevant safety data will be collected and reported per local regulations and EC/IRB requirements

---

**Medtronic Confidential**

This document is electronically controlled

056-F275, v3.0 Clinical Investigation Plan Template

## 4. Introduction

### 4.1. Background

Cardiovascular diseases are the leading cause of mortality in India, contributing to 25% of all mortality in the country. The Global Burden of Disease study estimate of age-standardized CVD death rate of 272 per 100,000 population in India is higher than the global average of 235 per 100,000 population [1].

#### Mitral valve regurgitation

One of the important pathologies seen in patients with cardiovascular disease is mitral valve regurgitation and insufficiency. Patients might suffer from different types of mitral valve dysfunction leading to different levels of regurgitation. The following classification of dysfunctional valves was introduced by Carpentier [2]:

- Type I: the free edges of the leaflets remain below the plane of the annulus during systole and open normally during diastole;
- Type II: the free edge of one or both leaflets overrides the plane of the annulus during systole;
- Type III: one or both leaflets do not open fully during diastole or close fully during systole
  - IIIa: restricted leaflet motion during systole and diastole
  - IIIb: restricted leaflet closure during systole

Type I dysfunction is the result of annular dilatation, often caused by myocardial infarction (MI). In most cases, type II dysfunction is a result from rupture or elongation of either the papillary muscles or the chordae tendinae, possibly as a result of MI. Type IIIa is mostly caused by leaflet thickening/retraction, chordal thickening/shortening/fusion or commissural fusion. Type IIIb dysfunction is the most common form of ischemic mitral regurgitation (IMR) [3].

Apart from the types of valve dysfunction, the severity of regurgitation can be gauged as per ASE guidelines [4] (see Table 1).

# PRESERVE-Mitral Clinical Investigation Plan

MDT16016SUR002

Version 1.0, dated 10-APR-2017

Page 12 of 58

Medtronic

**Table 1: ASE Guidelines for MR Severity Grading with Echocardiography [4]**

MR Severity*			
	Mild	Moderate	Severe
Structural			
MV Morphology	None or mild leaflet abnormality (e.g., mild thickening, calcifications or prolapse, mild tenting)	Moderate leaflet abnormality or moderate tenting	Severe valve lesions (primary: flail leaflet, ruptured papillary muscle, severe retraction, large perforation; secondary: severe tenting, poor leaflet coaptation)
LV and LA size†	Usually normal	Normal or mild dilated	Dilated‡
Qualitative Doppler			
Color flow jet area§	Small, central, narrow, often brief	Variable	Large central jet (>50% of LA) or eccentric wall-impinging jet of variable size
Flow convergence	Not visible, transient or small	Intermediate in size and duration	Large throughout systole
CWD jet	Faint/partial/parabolic	Dense but partial or parabolic	Holosystolic/dense/ triangular
Semiquantitative			
VCW (cm)	<0.3	Intermediate	≥0.7 (>0.8 for biplane)
Pulmonary vein flow#	Systolic dominance (may be blunted in LV dysfunction or AF)	Normal or systolic blunting#	Minimal to no systolic flow/ systolic flow reversal
Mitral inflow**	A-wave dominant	Variable	E-wave dominant (>1.2 m/sec)
Quantitative††,‡‡			
EROA, 2D PISA (cm  )	<0.20	0.20-0.29	0.30-0.39
RVol (mL)	<30	30-44	45-59††
RF (%)	<30	30-39	40-49
RVol (mL)			
RF (%)			

ROA, Regurgitant orifice area.

Bolded qualitative and semiquantitative signs are considered specific for their MR grade.

\*All parameters have limitations, and an integrated approach must be used that weighs the strength of each echocardiographic measurement. All signs and measures should be interpreted in an individualized manner that accounts for body size, sex, and all other patient characteristics.

†This pertains mostly to patients with primary MR.

‡LV and LA can be within the “normal” range for patients with acute severe MR or with chronic severe MR who have small body size, particularly women, or with small LV size preceding the occurrence of MR.

§With Nyquist limit 50-70 cm/sec.

||Small flow convergence is usually <0.3 cm, and large is ≥ 1 cm at a Nyquist limit of 30-40 cm/sec.

¶For average between apical two- and four-chamber views.

#Influenced by many other factors (LV diastolic function, atrial fibrillation, LA pressure).

\*\*Most valid in patients >50 years old and is influenced by other causes of elevated LA pressure.

††Discrepancies among EROA, RF, and RVol may arise in the setting of low or high flow states.

‡‡Quantitative parameters can help subclassify the moderate regurgitation group.

**Medtronic Confidential**

This document is electronically controlled

056-F275, v3.0 Clinical Investigation Plan Template

## Mitral valve repair – global perspective

Mitral valve repair is established as a procedure to alleviate mitral valvular insufficiency/stenosis. The pathophysiology of mitral valve insufficiency can be ischemic, rheumatic, degenerative, congenital, infective, myxomatous, etc.

Mitral valve repair may lead to better outcomes as compared to replacement. The overall survival of patients undergoing valve repair was found to be significantly superior to that of patients undergoing valve replacement, with 5- and 10-year survival rates, respectively, of  $83\pm3\%$  and  $68\pm6\%$  (repair, n=195) and  $69\pm3\%$  and  $52\pm4\%$  (replacement, n=214) [5].

Western studies on mitral valve repair have typically focused on patients with ischemic pathophysiology. In a study of patients with chronic moderately severe to severe mitral regurgitation (grade 3-4) and ischemic or dilated cardiomyopathy, all 121 patients underwent mitral valve repair (8 with a flexible ring; 113 with a semi-rigid ring) with concomitant surgery. The 30-day mortality was 3.3% and survival rates at 3 and 30 months were 95% and 91% respectively. At discharge, all 117 patients had MR level of 2 or less. No difference was found between patients implanted with flexible and semi-rigid annuloplasty rings [6].

One group of researchers investigated leaflet curvature and stress distribution of the mitral valve using numerical and experimental data and found that "it seems reasonable to hypothesize that a saddle-shaped annuloplasty ring may increase mitral valve repair durability by reducing leaflet and chordal strain". The shape of Medtronic's Profile 3D ring exactly matches the shape described by the authors [7].

## Guidelines

Current ACC/AHA guidelines [8] state that mitral valve repair is recommended in preference to mitral valve replacement in certain patients with chronic severe primary MR limited to posterior leaflet, or involving the anterior leaflet or both leaflets when a successful and durable repair can be accomplished. Concomitant repair is indicated for patients with chronic severe primary MR if they undergo cardiac surgery.

Mitral valve repair is considered reasonable in asymptomatic patients with chronic severe primary MR with preserved LV function, and reasonable as a concomitant procedure in patients with chronic moderate primary MR when undergoing cardiac surgery for other indications. Mitral valve surgery (including either repair, commissurotomy or replacement) may be considered in patients with rheumatic mitral valve disease when surgical treatment is indicated.

The guidelines also state that mitral valve surgery is indicated for severely symptomatic patients with severe mitral stenosis who are not at risk for surgery and who are not candidates for or have failed previous percutaneous mitral balloon commissurotomy.

## Regional perspective

Despite the guidelines, there may be local and regional differences in the standard practice in different geographies. While there are some Indian studies that have looked into mitral valve repair [9], [10], [11], there is still a need to gather more local evidence on clinical outcomes at long term follow up (12 months).

**Table 2: Indian studies on mitral valve repair procedures**

	Gupta, et al (2010) [9]	Choudhary, et al (2001) [10]	Saravana, et al (2015) [11]
Sample Size	n = 44	n = 818	n = 163
Prospective/Retrospective	Prospective	Retrospective	Prospective
Disease type	100% rheumatic	88% rheumatic 6% congenital 4% myxomatous 1% infective 1% ischemic	43% rheumatic 25% degenerative 21% ischemic 9% congenital 1% subacute bacterial endocarditis 1% other
Lesion type	45% pure MR 39% MR+MS 16% pure MS	53% pure MR 47% MR+MS	94% >=grade 3 MR 6% MR+MS
NYHA class	91% NYHA III/IV	64% NYHA III/IV 14% with congestive HF	88% NYHA III/IV

The significant proportion of mitral valve repair patients in India have rheumatic disease. Mitral valve repair is more technically challenging in this population, and is associated with higher failure rate. [10].

It is estimated that rheumatic heart disease prevalence is in the range of 1.5 to 2 per 1000 individuals (2–2.5 million cases in absolute numbers) in India, with an estimated 88,674 deaths (7 per 100,000 population) in the year 2010 [1].

The Global Rheumatic Heart Disease Registry (REMEDY study) enrolled patients presenting with rheumatic disease in 12 African countries, Yemen and India [12]. The patients with rheumatic heart disease were young (median age 28 years) and largely female (66.2%). The majority (63.9%) had multivalvular disease complicated by congestive heart failure. The majority of cases of mitral stenosis (72.9%) and mitral regurgitation (60.4%) had moderate-to-severe disease. A stark finding was that the utilization of valve surgery and valvuloplasty in patients with rheumatic heart disease in low-middle-income countries like India was 27.8%. Amongst the patients having native rheumatic valve disease with no percutaneous or surgical interventions, it was found that children in the first decade of life presented mostly with pure mitral regurgitation, and in the second decade of life, presented with mixed mitral and aortic valve disease with dominant mitral lesion [12].

Given this background, it is clear that the significant body of evidence for mitral valve annuloplasty from the west may not give a realistic picture of patients undergoing the same procedure in South Asia. Due to the difference in disease pathophysiology, the significant population of patients with rheumatic disease and differing surgical practice, there is a need to conduct a geography-specific study to understand the clinical outcome of patients undergoing mitral valve annuloplasty in the region. PRESERVE-Mitral, a

prospective registry to study long term performance of annuloplasty systems is thus proposed to document clinical outcomes, physician practice and report on outcomes in these patients.

## 4.2. Purpose

There is limited local evidence on mitral repair products in South Asia and a prospective post-market registry will provide real world data on clinical outcomes.

# 5. Objectives and Endpoints

## 5.1. Objectives

### 5.1.1. Primary Objective(s)

The objective of this registry is to gather data on the clinical outcomes of Medtronic mitral repair products (Profile 3D™ and CG Future® annuloplasty systems) in the approved intended use up to 12 months from the day of procedure.

### 5.1.2. Secondary Objective(s)

Characterize the demographics of the patients undergoing mitral valve repair using annuloplasty systems in South Asia, and assess the functional and procedural outcomes of the procedure.

## 5.2. Endpoints

### 5.2.1. Primary Endpoint

To evaluate clinical outcomes at 12 months post procedure:

1. Improvement in MR (grade)

This will be determined by assessing the level of mitral valve regurgitation using echo, in subjects at 12 months post procedure compared to the level at baseline. The levels of regurgitation, level 0-4, will correspond to the ASE guidelines ranging from no MR, Mild MR, Moderate MR, Moderate-to-Severe MR and Severe MR, as described in Table 1 above.

2. All cause mortality

All deaths occurring from any cause post procedure.

### 5.2.2. Secondary Endpoint(s)

- Characterization of patient demographics and pathophysiology of mitral valve disease

The patients will be identified by collecting the following patient characteristics at baseline: age (in years), gender, previous cardiovascular surgery, symptoms of heart failure, cardiac rhythm,

New York Heart Association (NYHA) classification, risk factors, level of regurgitation, type of mitral valve deficiency, etc.

- Improvement in MR grade at discharge and first follow up (3-6 months)

This will be determined by assessing the level of mitral valve regurgitation using echo, in subjects at discharge and 3-6 months post procedure compared to the level at baseline. The levels of regurgitation, level 0-4, will correspond to the ASE guidelines ranging from no MR, Mild MR, Moderate MR, Moderate-to-Severe MR and Severe MR, as described in Table 1 above.

- Improvement in NYHA functional class at discharge, first follow up (3-6 months) and second follow up (12 months) compared to baseline

The New York Heart Association (NYHA) Functional Classification is a system for defining cardiac disease and related functional limitations into four broad categorizations as defined in Table 3 below.

**Table 3: NYHA functional class definitions**

Classification	Description
Class I	Patients with cardiac disease, but without resulting limitations of physical activity. Ordinary physical activity does not cause undue fatigue, palpitation, dyspnea, or anginal pain.
Class II	Patients with cardiac disease resulting in slight limitation of physical activity. Patients are comfortable at rest. Ordinary physical activity results in fatigue, palpitation, dyspnea, or anginal pain.
Class III	Patients with cardiac disease resulting in marked limitation of physical activity. Patients are comfortable at rest. Less than ordinary physical activity causes fatigue, palpitation, dyspnea, or anginal pain.
Class IV	Patients with cardiac disease resulting in inability to perform any physical activity without discomfort. Symptoms of cardiac insufficiency or of the angina syndrome may be present even at rest. If any physical activity is undertaken, discomfort is increased.

- Hospitalization for Heart Failure at 6 months and at 12 months post procedure

Hospitalizations for Heart Failure are defined as a non-elective hospital admission for signs and symptoms related to heart failure that results in a one-night stay (i.e., where the admission date and the discharge date differ by at least one calendar day). For the purpose of the protocol, overnight stays at nursing home facilities or extended care facilities do not meet the protocol definition of hospitalization. The occurrence of hospitalization for heart failure will be evaluated at 6 months and 12 months post procedure.

- Mitral valve re-intervention at discharge, 6 months and at 12 months post procedure

Following the completion of the procedure, defined as the subject leaving the operating theater with an implanted Profile 3D™ or CG Future® annuloplasty system, any surgical or percutaneous interventional catheter procedure that repairs, otherwise alters or adjusts, or replaces the previously implanted annuloplasty system will be termed re-intervention. In addition to surgical

reoperations, enzymatic, balloon dilatation, interventional manipulation, repositioning, or retrieval, and other catheter-based interventions for valve-related complications are also considered re-interventions. The re-intervention rate will be evaluated at discharge, 6 months and 12 months post procedure.

- Stroke at 6 months and at 12 months post procedure

Stroke is defined as an acute episode of focal or global neurological dysfunction caused by brain, spinal cord, or retinal vascular injury as a result of hemorrhage or infarction, where the neurological dysfunction lasts for greater than 24 hours. The occurrence of stroke will be evaluated at 6 months and 12 months post procedure.

- New onset of Atrial Fibrillation, as evaluated through follow up ECG at discharge, first follow up (3-6 months) and at second follow up (12 months)

New onset of AF is defined as when the subject did not present with prior history of AF at baseline nor was AF detected at baseline visit, but AF did manifest post procedure and was either diagnosed during the study visits (discharge, 3-6 months or 12 months visit) or was otherwise diagnosed during the duration of subject participation in the study. The incidence of new onset AF will be evaluated at discharge, first follow up (3-6 months) and at second follow up (12 months).

- Number of attempts required for procedural success, and bypass time as a measure of procedural complexity, as measured by standard operating room procedures at the site.

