## **12. Data Review Committees**

There will be no Data Monitoring Committee (DMC) or Clinical Events Committee (CEC) used in this study. There will be a Medical Advisor assigned to this study, who will provide guidance on safety issues when escalated from the safety representative and is consulted on planning and documentation for the study. The contact information will be kept in the study roster.

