## 6. Determination of Sample Size

The sample size of 200 subjects who are eligible and intended to be implanted with a Profile 3D™ or CG Future® Annuloplasty system in the surgical repair procedure is adequate and appropriate for the evaluation of local evidence and obtaining real world data on clinical outcomes following implantation of these two products. This sample size was not statistically derived as this is not a hypothesis driven study.

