### 7.2 General Methodology

Descriptive statistics will be used to report study data. For continuous variables (e.g. age), the mean, median, standard deviation, minimum, maximum, and first and third quartiles will be presented. For categorical variables, the number and percentage of subjects in the category of interest will be presented. For time to event data, Kaplan-Meier analyses of event or event-free rates at discharge, 6 and 12 months will be presented. For these analyses, the time points will correspond to 7 days, 183 days and 365 days post implantation respectively. At each time point with data, the product limit estimate of the event or event-free rates, and the loglog transformed 95% confidence interval using the Peto standard error will be presented. For subjects without an event, the date of censoring will be the latest date of all follow-up visits (including phone and/or mail correspondence), assessments, events (including death) and study exits. For subjects whose exit reason is lost to follow-up, the last follow-up date will be the latest date of the follow-up visits (including phone and/or mail correspondence), assessments and events.

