**7.9.6 Secondary Endpoint #4**

Hospitalization for Heart Failure at 6 and 12 months post procedure.

Hypothesis/Decision criteria:

No specific hypotheses or pass/fail criteria have been set. The analysis will be descriptive and no statistical hypothesis test will be performed.

Endpoint Definition/Parameters to Be Estimated:

Hospitalization for Heart Failure event rate estimate will be provided at 6 and 12 months post procedure.

Data Collection and Analysis Dataset:

Data will be collected on an AE CRF.

This objective will be analyzed for the Successfully Implanted (IMP) cohort.

Analysis Method:

A Kaplan-Meier analysis will be performed.

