**7.9.8 Secondary Endpoint #6**

Stroke at 6 and 12 months post procedure.

Hypothesis/Decision criteria:

No specific hypotheses or pass/fail criteria have been set. The analysis will be descriptive and no statistical hypothesis test will be performed.

Endpoint Definition/Parameters to Be Estimated:

Stroke event rate estimate will be provided at 6 and 12 months post procedure.

Data Collection and Analysis Dataset:

Data will be collected on an AE CRF.

This objective will be analyzed for the Successfully Implanted (IMP) cohort.

Analysis Method:

A Kaplan-Meier analysis will be performed.

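### The stroke and HF-hospitalization definitions set a minimum duration with no provision for death, so rapidly fatal cases fall outside two secondary event rates

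*Combined protocol and SAP*

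**What the plan says.** CIP 5.2.2 defines both endpoints with a minimum duration. A stroke is an acute vascular neurological episode "where the neurological dysfunction lasts for greater than 24 hours". An HF hospitalization is a non-elective admission for heart failure with a one-night stay, "where the admission date and the discharge date differ by at least one calendar day". Neither definition mentions death, and the second does not say which date stands as the discharge date for a subject who dies in hospital.

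The SAP gives no definition of its own. Section 7.9.8 says only "Stroke event rate estimate will be provided at 6 and 12 months post procedure", and section 7.9.6 only "Hospitalization for Heart Failure event rate estimate will be provided at 6 and 12 months post procedure". Both take their data from the AE CRF and call for a Kaplan-Meier analysis in the Successfully Implanted set. Under SAP 7.2 a subject without an event is censored at the latest of all follow-up visits, assessments, "events (including death) and study exits".

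CIP section 12 states "There will be no Data Monitoring Committee (DMC) or Clinical Events Committee (CEC) used in this study". The second primary endpoint, in CIP 5.2.1, covers "All deaths occurring from any cause post procedure".

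**The concern.** A minimum duration separates lasting events from brief ones only if the subject survives long enough to meet it. Where the event kills first, the same limit removes a severe case. Followed as written, the plan treats a subject who dies of a stroke within 24 hours as stroke-free up to death, and treats a subject who dies on the date of an HF admission as never hospitalized for HF.

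The setting makes such cases possible. CIP 10.1 names thromboembolism, anticoagulant-related bleeding, low cardiac output and death among the known complications. The sponsor did provide for death in another endpoint: for NYHA class, CIP 13.6 and SAP 7.9.5 include died as an outcome category. Stroke and HF hospitalization have no counterpart.

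In a registry without hypothesis tests the estimated rates are the product, so what counts as an event matters even when numbers are small.

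**Working it through.** **1. The rules applied to four cases.** The clock times are illustrative.

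| Case | Test in CIP 5.2.2 | Result | Handling in SAP 7.2 |
|---|---|---|---|
| Stroke, death 10 hours after onset | Deficit beyond 24 h? No | Not a stroke event | Censored at death |
| HF admission 06:00, death 22:00 same date | Dates differ by 0 days | Not an HF event | Censored at death |
| HF admission 22:00, death 02:00 next date | Dates differ by 1 day, if the date of death serves as discharge date | HF event | Event |
| Death from heart failure during the index surgical stay | No new non-elective HF admission | Outside the endpoint under any wording | Not affected |

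The gap therefore covers strokes fatal within 24 hours of onset, and non-elective HF admissions with death on the admission date.

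**2. Direction.** In the product-limit estimate, a subject who leaves the risk set at a given time contributes a factor below 1 if counted as an event and no factor if censored. Reclassifying such a death from censored to event leaves the later risk sets essentially unchanged, so the estimated event rate can only rise. Applied uniformly, the literal rule can only understate.

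**3. Size.** The plan has no figure to reproduce. It gives no expected rate for either endpoint, and of the 200 subjects SAP section 6 says "This sample size was not statistically derived as this is not a hypothesis driven study". The following is illustration only.

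Inputs: N = 200 (CIP 13.4, SAP 6), all implanted and followed to 12 months (assumed); s = strokes lasting more than 24 hours (assumed 2 to 8); k = strokes fatal within 24 hours (assumed 0 to 3).

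- Rule as written, with the k deaths close to implant: about s/(200 − k)
- With death counted: (s + k)/200
- Relative understatement: 1 − [s/(200 − k)] / [(s + k)/200]

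| s | k | As written | Death counted (exact 95% CI) | Difference, points | Relative |
|---|---|---|---|---|---|
| 2 | 1 | 2/199 = 1.01% | 3/200 = 1.50% (0.31–4.32) | 0.49 | 33% |
| 2 | 3 | 2/197 = 1.02% | 5/200 = 2.50% (0.82–5.74) | 1.48 | 59% |
| 4 | 1 | 4/199 = 2.01% | 5/200 = 2.50% (0.82–5.74) | 0.49 | 20% |
| 4 | 2 | 4/198 = 2.02% | 6/200 = 3.00% (1.11–6.42) | 0.98 | 33% |
| 8 | 1 | 8/199 = 4.02% | 9/200 = 4.50% (2.08–8.37) | 0.48 | 11% |
| 8 | 3 | 8/197 = 4.06% | 11/200 = 5.50% (2.78–9.63) | 1.44 | 26% |

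With k = 0 nothing changes. If the deaths come late in follow-up, the as-written rate is closer to s/200 and each case costs 1/200 = 0.5 points. The same arithmetic serves HF admissions fatal on the admission date. The intervals are Clopper-Pearson, used here for scale; SAP 7.2 specifies log-log Kaplan-Meier limits with the Peto standard error.

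**The case against.** The strongest reply is that little is lost. These deaths count in the second primary endpoint and are serious adverse events under CIP 11.1. SAP 7.10 lists adverse events for all attempted-implant subjects and summarizes them by MedDRA term, independently of the duration rules in CIP 5.2.2. That stands, and it confines the effect to two secondary, descriptive estimates with no comparator or pass/fail criterion.

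A second reply is that understatement is not certain. Both endpoints come from the AE CRF, and the documents do not show how its terms are mapped to endpoints. A site may well report an early fatal cerebral haemorrhage as a stroke. That also stands, but such a site departs from the written definition. With 10 centers and no Clinical Events Committee, another site may not. The alternative to a consistent undercount is an inconsistent count.

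Third, sampling error dwarfs the effect: the exact interval for 5/200 spans 5.74 − 0.82 = 4.92 points, about ten times the 0.49 points for one case. This is true, but the interval does not correct an error that runs in one direction.

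Three stronger readings are tempting, and the documents do not support them. A reader might infer that MACCE component counts are wrong as well. CIP 11.1 lists stroke and HF hospitalization as MACCE components without importing the duration rules, and neither CIP section 13 nor the SAP plans a MACCE analysis. A reader might take a particular relative bias as established, but every percentage in the relative column follows from assumed counts. A reader might also treat all in-hospital HF deaths as excluded, when only new non-elective admissions with death on the same calendar date are affected.

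**Conclusion.** The gap is real on the text. Nothing in the CIP or SAP says how to classify death before the minimum duration, and the literal rule turns such cases into censored observations in the stroke and HF-hospitalization analyses. Followed literally, the two rates can only be understated; followed loosely, they may be counted differently across sites.

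The effect is about 0.5 percentage points per case in 200 subjects. If fewer than 200 are implanted, each case weighs slightly more. The number of cases is assumed to be zero to a few; under the assumed s = 2 to 8 and k = 1 to 3 the shortfall is about 0.5 to 1.5 points. The mortality endpoint and the SAP 7.10 adverse-event outputs are unaffected. This is a modest correction to two secondary endpoints, worth making because it is cheap and concerns severe events.

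**What to change.** Add one clause to each endpoint definition in the SAP:

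- SAP 7.9.8: a stroke counts if the deficit persists beyond 24 hours, or if the subject dies within 24 hours of its onset.
- SAP 7.9.6: an HF hospitalization counts if the stay spans at least one change of calendar date, or if the subject dies during that admission.

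Record both in SAP 7.12 as changes from the CIP. That section already carries a comparable change, to the atrial fibrillation endpoint. Apply the same rule when AE CRF terms are mapped to the endpoints, and bring CIP 5.2.2 into line at its next amendment. CIP 13.6 also summarizes the duration of HF hospitalization, so state that a same-date death enters that summary with zero nights.

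The cost is two clauses and a programming note. The reported rates may be slightly higher. A CIP edit may need EC/IRB submission under CIP 15.6, at 10 centers in three countries; making the change in the SAP first avoids waiting for that.
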